8 STUDY OBJECTIVES

Objectives for the OLE Phase are provided in [Appendix 6](#). (revised per Amendment 07)

8.1 Primary Objective

(revised per Amendment 05)

The primary objective is:

- To assess the safety (including immunological and hematological parameters) and tolerability of daily dosing with elenbecestat (E2609) in MCI/Prodromal subjects and in subjects with mild to moderate AD (revised per Amendment 01)

8.2 Secondary Objectives

The secondary objectives are: (revised per Amendments 02 and 05)

- To characterize the plasma and CSF PK of elenbecestat
- To assess the effects of elenbecestat on A β (1-x) and A β (1-42) in CSF from 4 weeks and at 18 months of treatment

8.3 Exploratory Objectives

(revised per Amendments 01,02, 04, and 05)

The exploratory objectives are:

To explore the effects of elenbecestat (E2609) compared on CSF A β (1-40) and BACE1 measurements from 4 weeks and up to 18 months of treatment

To explore the effects of elenbecestat (E2609) compared with placebo on various biomarkers. Biomarkers to be explored may include, but not limited to:

- a. CSF biomarkers of neurodegeneration (eg, total tau [t-tau], phosphorylated-tau [p-tau]) after 18 months of treatment
- b. Plasma and CSF amyloid, and CSF BACE1 measurements from 4 weeks and up to 18 months of treatment (revised per Amendment 06)
- c. Total hippocampal atrophy at 12 and 18 months of treatment, as measured by volumetric magnetic resonance imaging (vMRI)
- d. vMRI measurements including left and right hippocampal volume, whole brain volume, and total ventricular volume at 6, 12, and 18 months of treatment
- e. Brain amyloid levels at 18 months as measured by amyloid positron emission tomography (PET)

To explore the effects of elenbecestat (E2609) compared with placebo on clinical status at various time points during 18 months of treatment, and during posttreatment follow-up by assessment of:

-
- a. The Alzheimer's Disease Assessment Scale – cognitive subscale (ADAS-cog₁₄)
 - b. The Clinical Dementia Rating (CDR) scale
 - c. The Mini-Mental State Examination (MMSE)
 - d. The International Shopping List Task (ISLT)
 - e. The CogState Brief Battery (CBB)
 - f. The Functional Assessment Questionnaire (FAQ; (also known as the Functional Activities Questionnaire)

To explore the relationship between the treatment effects of elenbecestat (E2609) on measured clinical efficacy scales (eg, MMSE, CDR) and its effects on CSF amyloid, CSF amyloid isoforms, brain amyloid, and vMRI

To explore relationships between both elenbecestat (E2609) dose and exposure, with PD and safety endpoints

9 INVESTIGATIONAL PLAN

9.1 Overall Study Design and Plan

This study is a multicenter, placebo-controlled, double-blind, parallel-group, randomized, dose-finding study with an OLE Phase of up to 27 months in subjects with MCI/Prodromal AD or mild to moderate AD. (revised per Amendments 01 and 07)

A common set of inclusion criteria, consistent with the NIA-AA clinical research criteria for MCI due to AD or mild to moderate AD, will be required for all subjects. In addition, the MCI due to AD population will also be consistent with the research criterion for “Prodromal AD” in that episodic memory will be impaired on a list learning task (ISLT). As the non-demented subjects will be consistent with criteria for both MCI due to AD and Prodromal AD they will be identified as MCI/Prodromal subjects in this protocol. The diagnosis of MCI/Prodromal AD or mild to moderate AD will be based on both clinical and biological (ie, confirmation of amyloid load in the brain) criteria. (revised per Amendment 01)

The study consists of 3 phases: Prerandomization, Randomization, and OLE. The Prerandomization and Randomization Phases are referred to as the Core Study throughout the protocol. (revised per Amendment 07).

The Prerandomization Phase (up to 60 days, plus an additional window of up to 30 days if required [revised per Amendment 02]) will consist of a Screening Visit and a Baseline Visit. Screening assessments will be organized into 4 tiers; see [Section 9.5.2.2](#), [Table 6](#), and [Figure 2](#).

All screening assessments must be completed, and eligibility to continue to the Baseline Period confirmed, before any baseline assessments commence. Following successful completion of the Prerandomization Phase, eligible subjects will be randomized and will enter the Randomization Phase, which will consist of 2 periods: Treatment (78 weeks) and Follow-Up (post last dose; 12 weeks).

All subjects (MCI/Prodromal and mild to moderate AD) will initially be randomized 1:1:1:1 to 4 treatment groups (5, 15, or 50 mg elenbecestat [E2609] or placebo) (revised per Amendments 01 and 05). Upon implementation of Amendment 06, at the next regularly scheduled visit, subjects receiving elenbecestat (E2609) 5 or 15 mg who have not yet completed Visit 17 (Week 66), will be re-assigned in a blinded manner to elenbecestat (E2609) 50 mg for the remainder of the treatment period. In order to maintain the blind, all subjects who have not yet had Visit 17 will go through the same procedures with the placebo-randomized subjects continuing to receive placebo and those randomized to elenbecestat (E2609) 50 mg continuing to receive 50 mg. (revised per Amendment 06)

All subjects who complete 18 months of treatment and 12 weeks of follow-up in the Core Study and who satisfy the entry criteria for the OLE Phase are eligible to enter the OLE Phase. During the OLE Phase, subjects will receive elenbecestat (E2609) 50 mg daily for up to 24 months (2 years).

An overview of the Core Study design is presented in [Figure 1](#).

[figure not shown]

Figure 1 Design of Core Study E2609-G000-202

(revised per Amendments 01, 02, 05, and 06)

R = randomization, AD = Alzheimer’s Disease, MCI = mild cognitive impairment.

This study will be limited to approximately 35 sites in the United States, with approximately 60 ($\pm 20\%$) eligible subjects randomized at Visit 3, 1:1:1:1 to 4 treatment groups within each clinical cohort. In addition to the placebo group, 3 doses of elenbecestat (E2609) will be used to reduce CSF A β levels by approximately 25% (5 mg), 50% (15 mg), and 75% (50 mg) from baseline, respectively, at steady state. PK/PD modeling shows these doses should achieve these targets when administered QD with food and will be evaluated based on the 4-week (or later) assessment of CSF A β (1-x) from subjects who provide voluntary consent for CSF measurement (see [Section 9.4.4](#)). (revised per Amendments 01, 02, 04, and 05) Safety data will be monitored in a blinded fashion on a regular basis.

In addition, approximately every 3 months from the time the 1st subject is randomized into the study through the time the last subject is randomized, an independent DSMB (including at least 1 immunologist) will review all safety data in an unblinded manner. (revised per amendment 06) The DSMB will make recommendations to Eisai after each review as to whether any change(s) to the study are necessary. (revised per Amendments 01, 04, and 05)

Subjects who initially consented to CSF collection and provided a baseline CSF sample but did not provide a postrandomization sample will be approached to consider reconsenting to postrandomization CSF sample collection even if they are beyond Week 5 (Visit 7); however, subject re-consent to this procedure is optional for these subjects. (revised per Amendment 04)

Interim analyses of the elenbecestat (E2609) plasma PK for all subjects and the elenbecestat (E2609) CSF PK and PD profiles will be performed on baseline data and samples collected after at least 4 weeks of treatment in the Core Study. (revised per Amendment 05 and 07) Refer [Section 9.7.3](#) for more detail. These data will be used to evaluate the CSF PD effects of elenbecestat (E2609) doses, where PD is measured as reductions from baseline in CSF A β (1-x) levels (see [Section 9.4.4](#)). The median and mean percentage change from baseline in CSF A β (1-x) measured after 4 weeks or more of treatment for each dose of elenbecestat (E2609) and the 90% confidence interval (CI) for the median will be derived. In addition, exploratory PK/PD modeling will be conducted. This PK/PD modeling will use the observed PK and PD data and will relate the average steady state plasma concentration of elenbecestat (E2609) to steady state CSF A β (1-x) percentage reduction from baseline determined after at least 4 weeks of dosing. (revised per Amendments 01, 02, 03, and 04)

Once subjects have completed at least 12 weeks of treatment in the Core Study (or discontinued study drug early), an interim safety analysis will be conducted by Eisai and the DSMB. (revised per Amendments 01, 04, and 05) At the completion of this interim safety review, the frequency of subsequent unblinded safety reviews will be re-evaluated by the DSMB and the Sponsor and this information will be provided in the DSMB charter. (revised per Amendment 06) Subjects will continue study drug while the DSMB reviews all the available safety data. (revised per Amendment 05) At the time of this interim safety analysis, some subjects will have more than 12 weeks of safety data.

Interim analyses are planned and are discussed in [Section 9.7.3](#). (revised per Amendment 03)

Based on the results of the interim analyses, the elenbecestat (E2609) 50 mg dose has been chosen as the clinical dose for the Phase 3 studies. In order to collect additional safety data for elenbecestat (E2609) 50 mg, subjects randomized to elenbecestat (E2609) 5 or 15 mg in this study will be re-assigned to elenbecestat (E2609) 50 mg if and only if these subjects have at least 12 weeks of treatment remaining in the Randomization Phase following study drug dose re-assignment. Therefore, subjects who completed Visit 17 assessments prior to the implementation of Amendment 06 will remain on their original randomized dose. As study drug dose re-assignment will occur in a blinded manner, a 4-week interim safety assessment following study drug re-assignment will be required for all subjects. (revised per Amendment 06)

9.1.1 Prerandomization Phase

The Prerandomization Phase includes a Screening Visit and a Baseline Visit. All Screening Visit assessments must be completed and eligibility to progress must be confirmed before any Baseline Visit assessments are performed. All Screening Visit and Baseline Visit assessments must be completed within 50 days (plus an additional window of up to 30 days if required [revised per Amendment 02]) and a window of no more than 10 days is to be observed between the completion of all Baseline Visit assessments (including confirmation of eligibility following all Baseline Visit assessments) and randomization into the study at Visit 3 (revised per Amendment 02). Thus, the Prerandomization Phase will last for up to

60 days, plus an additional window of 30 days if required (revised per Amendment 02). The series of assessments conducted during this phase will determine eligibility for randomization into the study.

Inclusion criteria are discussed in [Section 9.1](#) and detailed in [Section 9.3.1](#). Before randomization, the clinician will provide a judgment on the classification of a subject as either MCI/Prodromal or likely mild to moderate AD. (revised per Amendment 01) This judgment may be discussed and reviewed with the Sponsor or Sponsor's representative, as necessary.

Results of the Screening safety magnetic resonance imaging (MRI) will be valid for 90 days from the date of scanning. Results of the lumbar puncture (LP) from subjects who voluntarily consent for CSF measurement will be valid for 90 days from the date of testing. Results of Screening PET scans conducted specifically for this study and for use in the longitudinal analyses will also be valid for 90 days from the date of scanning. These assessments will not need to be repeated should the subject be randomized within that time period either under their original subject identification number or under a new re-screening subject identification number. Historical PET scans used for determination of eligibility only (ie, not used for the longitudinal analyses) are valid for 12 months. (revised per Amendment 02)

9.1.1.1 Screening Period

The purpose of the Screening Period is to obtain informed consent and to establish protocol eligibility. Informed consent will be obtained after the study has been fully explained to each subject and caregiver or informant, and before the conduct of any screening procedures or assessments. Procedures to be followed when obtaining informed consent are detailed in [Section 5.3](#). No subject will undergo any further study procedures unless this informed consent has been obtained from both the subject and the caregiver or informant. The caregiver or informant needs to be present at this visit.

Study site personnel will interview the subject and caregiver or informant to obtain demographic and clinical information as described in [Table 6](#), and will review inclusion and exclusion criteria as described in [Sections 9.3.1](#) and [9.3.2](#) and perform any required assessments in order to complete these criteria. Prior medications and medications currently being taken by the subject will be reviewed (see [Section 9.4.7](#)). The Screening Disposition electronic case report form (eCRF) page must be completed to indicate whether the subject is eligible to participate in the study and to provide reasons for screen failure, if applicable.

Clinical assessments for eligibility will be conducted during the Screening Visit as described in [Table 6](#) and [Figure 2](#).

Every effort should be made to conduct these assessments in the morning, but if this is not possible, they should be conducted at the same time of day at all subsequent visits. The screening assessments/procedures have been organized into 4 distinct tiers ([Table 6](#) and [Figure 2](#)). All assessments/procedures in each tier should be completed, and eligibility to continue screening in the study confirmed, before any assessments/procedures from the next

tier commence. Tier 2 procedures may be performed on the same day as Tier 1 procedures as long as the results of all Tier 1 procedures (eg, delayed recall on the ISLT) show that the subject is eligible to continue with screening activities. (revised per Amendment 01)

[figure not shown]

Figure 2 Assessments to be Performed at Screening by Tier

CBB = CogState Brief Battery, CBP = childbearing potential, CDR = Clinical Dementia Rating, C-SSRS = Columbia Suicide Severity Rating Scale, ECG = electrocardiogram, FAQ = Functional Assessment Questionnaire (also known as the Functional Activities Questionnaire), ISLT = International Shopping List Task (immediate and delayed recall), MMSE = Mini Mental State Examination, MRI = magnetic resonance imaging, PET = positron emission tomography, TB = tuberculosis.

Cognitive assessments (Tier 1) are to be completed in the morning whenever possible, or consistently at the same time of day. These assessments should be completed before more invasive assessments/procedures (eg, physical examination, ECG, blood draws). The recommended order of assessments at Screening is: MMSE, ISLT (immediate recall), CBB, ISLT (delayed recall), CBB (repeat CBB for additional practice), CDR, and FAQ. The CBB may be repeated multiple times if required for the subject to pass completion and integrity criteria. (revised per Amendment 02) The investigator will determine whether the caregiver or informant must attend in person or whether telephone contact will be suitable, and will base this determination upon the functional ability of the subject among other factors.

Volumetric MRI for PD assessment will be performed in all subjects immediately following the safety MRI assessments in the same imaging session (Tier 3).

Amyloid PET imaging will be used to confirm all subjects have amyloid deposition in the brain (Tier 4). An historical amyloid positive PET scan may be used if conducted within the previous 12 months and provided that the scan and result are considered acceptable by the central PET reading group. If an historical amyloid positive PET scan is being used, it should be submitted to the central PET reading group after the subject has completed and passed all Tier 1 assessments. (revised per Amendment 02)

9.1.1.2 Baseline Period

All Screening Visit assessments must be completed (and eligibility to progress confirmed) before any Baseline Visit assessments are performed. The Baseline Visit assessments (per [Table 6](#) and [Section 9.5.1.2](#)) are to be completed as soon as possible after completion of the final Screening Visit assessment (ie, PET scan) such that all Screening Visit and Baseline Visit assessments are completed within 50 days, plus an additional window of up to 30 days if required. (revised per Amendment 02)

Inclusion and exclusion criteria will again be reviewed, vital signs including weight will be recorded, and a 12-lead ECG will be conducted in triplicate. A routine physical examination will be conducted and a dermatological assessment and neurological examination (including the Brief Smell Identification Test [Sensonics Inc.]) will be performed. (revised per Amendment 04) A urine pregnancy test will be conducted for females of childbearing potential. Blood will be collected from all subjects for clinical chemistry and hematology, lymphocyte subset analyses, Ig analyses, and PD assessments. Blood samples will be collected and stored for determination of a subject's previous exposure to infective pathogens in the event of AEs that warrant further investigation occurring at a later point in the study. Psychometric assessments will be administered to the subject in the order stated in [Table 6](#). The caregiver or informant needs to be present at this visit. The Columbia Suicide Severity Rating Scale (C-SSRS) will also be administered ([Section 9.5.1.5.11](#)).

For subjects who consent to CSF sample collection, a CSF sample will be obtained at this visit for PK and PD assessments (see [Section 9.5.1.4](#)). (revised per Amendment 02)

Subjects who initially consented to CSF collection and provided a baseline CSF sample but did not provide a postrandomization sample will be approached to consider reconsenting to postrandomization CSF sample collection even if they are beyond Week 5 (Visit 7); however, subject consent to this procedure is optional for these subjects. (revised per Amendment 04)

Blood will be collected from all subjects for pharmacogenomic (PGx) analyses of apolipoprotein E (*ApoE*) and the N-acetyltransferase 2 (*NAT2*) phenotype of subjects enrolled in the study (see [Section 9.7.1.7.2](#)).

9.1.2 Randomization Phase

Subjects who complete the Baseline Visit assessments, and are eligible based on the inclusion and exclusion criteria (see [Section 9.3.1](#) and [Section 9.3.2](#)), will begin the Randomization Phase no more than 10 days after completion of the Baseline Visit assessments and confirmation of the eligibility of the subject based on the results of all the Baseline Visit assessments (revised per Amendment 02).

The Randomization Phase will consist of a Treatment Period of 78 weeks duration and a Follow-up Period of 12 weeks after the last dose of study drug.

9.1.2.1 Treatment Period

Subjects will be randomized at the beginning of the Treatment Period and will receive study drug or placebo, to be administered orally QD with food. Double-blinding to study drugs will be in effect throughout the Treatment Period. (revised per Amendment 06)

Safety criteria for discontinuation of study drug are detailed in [Section 9.3.3](#).

Subjects will attend the study site every week for the first 4 weeks after beginning study drug, then fortnightly until 12 weeks have elapsed since first dose. Visits will then be conducted at 16, 20, 26, 39, 52, 65, and 78 weeks after the first dose.

9.1.2.2 Early Discontinuation

Subjects who discontinue taking study drug prematurely for any reason will undergo an Early Discontinuation (ED) Visit within 7 days of their last dose of study drug. Follow-Up Visits will also be scheduled 2, 4, 8, and 12 weeks after the last dose of study drug. (revised per Amendments 04 and 05)

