9.3.3 Removal of Subjects from Therapy or Assessment

The investigator may discontinue study drug or withdraw the subject from the study at any time for safety or administrative reasons. The subject may decide to stop study drug or withdraw from the study at any time for any reason.

Subjects who discontinue taking study drug prematurely for any reason will undergo an ED Visit within 7 days of their last dose of study drug (see [Section 9.1.2.2](#)). Follow-Up Visits will also be scheduled 2, 4, 8, and 12 weeks after the last dose of study drug in the Core Study (see [Section 9.1.2.3](#)), and 4 and 12 weeks after the last dose of study drug in the OLE Phase (see [Appendix 6](#)). (revised per Amendments 04, 05 and 07)

The primary reason for discontinuation and all other reason(s) contributing to the subject's discontinuation from study drug(s) should be collected on the Subject Disposition eCRF page. In addition, the date of last dose of study drug(s) will be recorded on the Study Drug Dosing eCRF page. If a subject discontinues study drug and withdraws from the study at the same time, the ED Visit will be followed (see [Section 9.5.5](#)).

Safety-related criteria for discontinuation of study drug during the Core Study include the following: (revised per Amendments 07)

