- a. A study drug discontinuation threshold will be set based on absolute counts of CD4 (T helper cells), CD8 (cytotoxic T cells), or CD19 (B cells). The discontinuation threshold will be set at below the level of the population-adjusted LLN (CD4=396 cells/ μ L; CD8=157 cells/ μ L; and CD19=74 cells/ μ L), at a level that represents a greater risk of opportunistic infection in the treated population. (revised per Amendment 02) For CD4 (T helper cells) the discontinuation threshold is 250 cells/ μ L. For CD8 (cytotoxic T cells) and CD19 (B cells) the discontinuation thresholds are 150 cells/ μ L and 50 cells/ μ L, respectively. Any subject who has CD4 (T helper cells), CD8 (cytotoxic T cells), or CD19 (B cells) absolute counts below the discontinuation threshold as confirmed by a repeat test conducted within 1 week of the initial test but who has no clinical signs or symptoms of infection, will have study drug temporarily suspended for at least 2 weeks but no more than 4 weeks. During this period of study drug suspension, lymphocyte subset counts and complete blood count (CBC) with differentials will continue to be tested weekly until CD4 (T helper cells), CD8 (cytotoxic T cells), and CD19 (B cells) have all returned to greater than the population-adjusted LLN after which time study drug can be resumed. Testing of lymphocyte subset counts and CBC with differentials is required weekly for 4 weeks following resumption of study drug administration. Temporary suspension and rechallenge with study drug is only permitted once for any given subject. If the lymphocytes and CD counts do not return to greater than the population-adjusted LLN within 4 weeks from the start of temporary suspension the subject will need to be permanently discontinued from study drug. (revised per Amendment 04)

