- f. Development of any of the following features on MRI: vasogenic edema, macrohemorrhage, an area of superficial siderosis, or a symptomatic microhemorrhage. If discontinued from study drug, subjects will undergo an ED Visit within 7 days after discontinuation and will attend the Follow-Up Visits 2, 4, 8, and 12 weeks after the last dose of study drug. They will also undertake an Unscheduled Visit (with MRI) at approximately 4 weeks after the visit at which such MRI features were first identified. An MRI will also be performed at approximately the time of the final Follow-Up Visit (Visit 20). Additional visits for safety may be arranged if clinically indicated in the opinion of the investigator, including after 12 weeks after the last dose of study drug. At any time during the treatment period, subjects who have asymptomatic, treatment-emergent microhemorrhages as detected by MRI, but none of the features which merit discontinuation of treatment (ie, vasogenic edema, macrohemorrhage, an area of superficial siderosis, or a symptomatic treatment-emergent microhemorrhage) may continue with treatment. These subjects will have safety assessments (including MRI) at approximately 4 weeks after the visit at which such MRI features were found. They will also continue with the scheduled MRI scans. Additional unscheduled MRI scans may be arranged on an individual subject basis in discussion with the study medical monitor. (revised per Amendment 04)
- g. A postdose ECG with an average QTcF interval >500 msec from triplicate ECGs
- h. A postdose ECG with a QTcF interval increase from baseline >60 msec and a QTcF interval >450 msec as demonstrated from triplicate ECGs
- i. Any seizure (motor or non-motor)
- j. Pregnancy

Safety-related criteria for discontinuation of study drug during the OLE Phase are provided in [Appendix 6](#). (revised per Amendment 07)

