| Randomization | X | | | | | | | | | | | | | | | | | | | | | | | | | | |
| Dispense study drug ^x | X | X | X | X | X | X | X | X | X | X | X | X | X | X | X | | | | | | | | | | | | |

Footnotes for Table 7

ADAS-cog₁₄ = Alzheimer's Disease Assessment Scale - Cognitive subscale (14 items), CBB = CogState Brief Battery, CBP = childbearing potential, CDR = Clinical Dementia Rating scale, CSF = cerebrospinal fluid, C-SSRS = Columbia Suicide Severity Rating Scale, ECG = electrocardiogram, ED = Early Discontinuation, FAQ = Functional Assessment Questionnaire (also known as the Functional Activities Questionnaire), Ig = immunoglobulin, ISLT = International Shopping List Task, LP = lumbar puncture, MMSE = Mini Mental State Examination, MRI = magnetic resonance imaging, PBMC = peripheral blood mononuclear cell, PD = pharmacodynamics, PET = positron emission tomography, PK = pharmacokinetics, UNS = unscheduled, W2 = new Week 2 follow-up visit, W8 = new Week 8 follow-up visit. (revised per Amendment 04)

- a: Visit 3 should be conducted no more than 10 days after completion of the Baseline visit (Visit 2) assessments and confirmation of eligibility to continue in the study, unless additional time is required to take Exclusion Criterion #20 into account. (revised per Amendment 02) A window of ± 3 days will be permitted for Visit 4 to 14 inclusive. A window of ± 10 days will be permitted for Visit 15 to 18 inclusive. A window of ± 3 days will be permitted for the Follow-Up Visits. If use is made of the permitted visit windows, every effort should be made to bring the subject back in line with the "weeks elapsed since first dose" at subsequent visits.
- b: Subjects who discontinue taking study drug prematurely for any reason will undergo an ED Visit within 7 days of their last dose of study drug. In addition, Follow-Up Visits will be scheduled 2, 4, 8, and 12 weeks after the last dose of study drug (Visit W2, 19, W8, and Visit 20, respectively). (revised per Amendments 04 and 05)
- c: All subjects, regardless of whether they complete all 18 months of treatment or discontinue study drug prematurely, will complete 4 posttreatment Follow-Up visits; 2, 4, 8, and 12 weeks after the last dose of study drug (Visits W2, 19, W8, and 20, respectively). If clinically indicated, more frequent safety assessments can be made as UNS assessments or visits during the posttreatment Follow-Up period. (revised per Amendment 04)

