- v: For subjects who consent to CSF sample collection: Postrandomization CSF sample collection is scheduled at Visit 7 (or later postrandomization timepoint) and Visit 18/ED. If a postrandomization CSF sample is collected later than Visit 7, time-matched plasma PK samples are also required (see Footnote t). All visits at which CSF samples are scheduled to be taken also include blood PK and PD assessments and so the subject will be dosed at the clinic on these days. The timing of the Baseline LP needs to be scheduled carefully such that subsequent LPs (Visit 7 [or later postrandomization timepoint] and Visit 18) can be performed between 4 and 8 hours postdose and at a similar time of day (± 1 hour) for each individual subject. The CSF sample will be taken with the subject fasting (preferred) or at least 2 hours after the most recent meal. A gravity drip collection method must be used. If the LP and the cognitive tests are performed on the same day, the LP must be performed after the cognitive tests have been completed and the subject should rest and drink some fluid to hydrate before the LP. Subjects will be encouraged to stay at the site after completion of LP for medical observation. The CSF sample will not be taken at the ED Visit if this visit occurs within 3 months of a previous CSF sample. If at an ED Visit, the subject has already

Footnotes for Table 7

stopped study drug, then no dosing will take place, but the CSF sample will still be collected unless it was already collected within the past 3 months. . Subjects who initially consented to CSF collection and provided a baseline CSF sample but did not provide a postrandomization sample will be approached to consider reconsenting to postrandomization CSF sample collection even if they are beyond Week 5 (Visit 7); however, subject re-consent to this procedure is optional for these subjects. (revised per Amendments 01, 02, and 04)

- w: Subjects reporting AEs relating to abnormal dreams, nightmares, or sleep terror will be questioned on the frequency and impact of these events.
- x: The first dose of study drug will be given to the subject at the study site and the subject will be encouraged to stay at the site for an appropriate period of time as determined by the PI or Safety Physician for postdose medical observation. (revised per Amendment 02)

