9.7.1.6.2 SECONDARY EFFICACY ANALYSES

An mixed-effects model with repeated measures (MMRM) will be used to analyze the following secondary endpoint:

- Change from baseline in CSF A β (1-x) and CSF A β (1-42) from 4 weeks and up to 18 months. Data from early discontinuations will also be included. (revised per Amendment 05)

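### After a failed lymphocyte suspension the Early Discontinuation visit falls due about 21 days after its window has closed, and any CSF taken there enters the on-treatment amyloid model while the subject is about 4 weeks off drug (minor)

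*Protocol*

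**What the plan says.** The ED visit is counted from the last dose for every premature discontinuation, whatever the reason. Section 9.1.2.2 says such a subject "will undergo an Early Discontinuation (ED) Visit within 7 days of their last dose of study drug". Section 9.3.3 (opening text), Section 9.5.5 and Table 7 footnote b give the same rule. Footnote b times the follow-up visits from the same date: "Follow-Up Visits will be scheduled 2, 4, 8, and 12 weeks after the last dose of study drug".

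Section 9.3.3(a) sets a different clock for one group. A subject whose CD4, CD8 or CD19 count is confirmed below the discontinuation threshold, without infection, "will have study drug temporarily suspended for at least 2 weeks but no more than 4 weeks". If counts have not risen above the population-adjusted lower limit "within 4 weeks from the start of temporary suspension the subject will need to be permanently discontinued from study drug". Section 9.5.5 treats temporary suspension and discontinuation as separate states.

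Section 9.3.3(f), on MRI findings, uses another starting point for the same visit: "subjects will undergo an ED Visit within 7 days after discontinuation".

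On CSF, Table 7 footnote v provides that where drug has already stopped before the ED visit, "the CSF sample will still be collected unless it was already collected within the past 3 months". Section 9.7.1.6.2 specifies a mixed model for change in CSF amyloid β(1-x) and β(1-42) and adds: "Data from early discontinuations will also be included". Section 9.7.1.1.2 words the matching secondary endpoint as a reduction after a period of treatment.

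**The concern.** Followed as written, the rules give a visit date that cannot be met. While suspended, the subject has not discontinued, so no ED visit is due. By the time failure to recover makes the stop permanent, the 7-day limit counted from the last dose has long passed. A site that complies fully still records a window deviation.

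The statistical consequence concerns the CSF. The secondary endpoint is the amyloid reduction achieved on treatment. A sample taken about 4 weeks after the last dose does not measure that, yet the protocol both collects it and places early-discontinuation data in the model with no limit on time off drug.

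**Working it through.** No sample size, power or error rate is involved. The check is day arithmetic on the stated rules. Day 0 is the last dose, taken as the start of suspension.

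**Inputs**
- ED limit: 7 days from last dose (9.1.2.2, 9.3.3, 9.5.5, Table 7 footnote b).
- Suspension: 14 to 28 days. A permanent stop for non-recovery comes at 28 days (9.3.3(a)).
- Follow-up visits: days 14, 28, 56 and 84 after last dose, each ±3 days (Table 7 footnotes a and b).
- Visit 7, the first scheduled post-randomization CSF: study Day 29 (Table 7).
- No ED CSF within 3 months of a previous sample (9.5.1.4.2, Table 7 footnote v).

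**ED visit**
- Permanent stop minus ED limit: 28 − 7 = 21 days late when first due.
- Even the minimum suspension outlasts the limit: 14 − 7 = 7 days.

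**Follow-up visits at day 28**
- Week 2: 14 ± 3 = days 11 to 17, already past.
- Visit 19 (week 4): 28 ± 3 = days 25 to 31, open.
- Week 8 (days 53 to 59) and Visit 20 (days 81 to 87): unaffected.

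**If ED were counted from the decision to discontinue**
- Window: day 28 to 28 + 7 = day 35.
- Overlap with Visit 19: days 28 to 31.
- The window can then be met, but the CSF is still 4 to 5 weeks off drug. Moving the visit does not solve the analysis problem.

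**Who could give such a CSF sample**
- With a Visit 7 sample, taking 3 months as 91 days: 29 + 91 = study Day 120 at the earliest, so the last dose falls at about 120 − 28 = Day 92 or later.
- The subject must also have consented to CSF sampling, which is voluntary.

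**How far off drug (side check under an assumption)**
- The Amendment 04 rationale in the revision history says PK steady state is reached within 2 weeks. The half-life is not given.
- If 14 days is 3.3 to 5 half-lives, the half-life is 14/3.3 = 4.24 days to 14/5 = 2.8 days.
- Residual drug = 0.5^(t / half-life). At day 7 this is 18% to 32%; at day 28 it is 0.1% to 1%.
- This describes drug level only. The documents give no rate for the return of CSF amyloid, and the timing conflict does not depend on this check.

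**The case against.** The strongest reply is that the timing half is close to editorial. The protocol foresees an ED visit after drug has stopped: Section 9.5.1.4.1 and Table 7 footnotes t and v omit dosing but still take PK and CSF samples. Those provisions change what is done at the visit and do not extend the 7 days. The wording in 9.3.3(f) that counts from discontinuation applies to MRI stops only. The date conflict therefore stands, although the consequence is only a late visit.

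The second reply is that mapping and off-drug rules belong in the statistical analysis plan, which is not at hand and may exclude these samples. That is fair for matters the protocol leaves open. Here the protocol states that early-discontinuation data go in, for an endpoint defined by time on treatment, so it has fixed the matter in a way that misfires in this pathway.

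Three stronger readings are tempting and are not supported.
- A reader might infer that week-2 safety assessments are lost. Section 9.3.3(a) requires weekly lymphocyte subsets and blood counts during suspension, footnote l adds adverse-event assessment to unscheduled subset tests, and Table 7's unscheduled-visit column offers vital signs, respiratory rate and concomitant medications at the investigator's discretion.
- A reader might want to put a number on the shift in the 50 mg mean. The documents give neither the number of CSF subjects at that time point nor the effect remaining at day 28. The Amendment 06 re-assignment of 5 and 15 mg subjects to 50 mg also changes the denominator.
- A reader might conclude that the ED lumbar puncture should be waived. That is a trade-off: the same sample supplies tau and BACE1 measurements and may be tested if adverse events need investigating, in subjects stopped for an immune signal.

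**Conclusion.** The point holds as a minor one. In this pathway the ED visit is about 21 days out of window when it first falls due, and an eligible subject's ED CSF, about 4 weeks off drug, enters a model meant to describe on-treatment amyloid reduction.

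The date conflict follows directly from the stated rules. It assumes that the stop is made permanent by the 4-week non-recovery rule; an investigator who stopped the drug for good within the first week of suspension could still meet the window.

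The number affected is not given and is probably small. Section 7.2 reports that lymphocyte effects in the multiple ascending dose study resolved 6 to 21 days after the last dose, inside the 28 days allowed here, though after only 14 days of dosing. The CSF consequence is narrower again, since it needs consent and no sample in the past 3 months. Visit 7 values are unaffected. The size of any effect on the model estimate cannot be derived from the documents.

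**What to change.** 1. In Sections 9.1.2.2, 9.3.3(a) and 9.5.5 and in Table 7 footnote b, state that when a temporary suspension becomes permanent the ED visit is held within 7 days of the decision to discontinue, as 9.3.3(f) already does for MRI stops. Combine it with Visit 19 where the windows overlap (days 28 to 31), and do not require the elapsed week-2 visit.

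2. In Section 9.7.1.6.2, state that ED CSF taken after a failed suspension is summarised separately as off-drug and is not used as an on-treatment value in the mixed model. The last-dose date needed to identify these samples is already recorded on the Study Drug Dosing eCRF.

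Both parts are needed, because the first alone leaves the CSF off drug. The cost is a few lines in an amendment, with no new visits or tests. The downside is that a few ED CSF values leave the model.
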